7.2.8 Early Treatment Termination Visit

The early treatment termination visit should be performed at any time during the study (\pm 14 days), if based on the clinical evaluation, the investigator suspects PD, or if the subject discontinues treatment for any other reason outlined in Section 5.6. If the subject comes in for a regular study visit and the investigator wants to discontinue treatment at that time, the regular visit will become the termination visit. Any additional procedures that would be performed for the regular study visit should be performed for the treatment termination visit. Adverse events and hospitalizations will be recorded up to 30 days after the last dose of study drugs.

The following procedures will be performed:

- Complete physical exam
- ECOG performance status
- Vital signs and weight
- Clinical laboratory tests for:
 - Hematology
 - Serum chemistry
 - TSH
- Research laboratory tests for:
 - Biomarkers
- Review of AEs and concomitant medications
- Drug accountability
- CT/PET/or MRI
- Optional tumor tissue biopsy to document PD (Research biomarker assessment)

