7.4.19 Tumor Tissue Biopsy

For subjects with PD on radiologic assessment, a tumor biopsy to confirm PD is optional. Tumor samples may be analyzed by gene expression profiling, immunohistochemistry, flow cytometry, or other methods to define biomarkers that predict response or resistance to lenalidomide, rituximab and ibrutinib therapy.

In consenting patients, core needle biopsies and fine needle aspirates (FNA) will be obtained at Screening by Interventional Radiology from accessible lymph node under ultrasound or CT-scan guidance. At the time of confirmed PD, if a tumor biopsy is planned as part of routine clinical practice, for consenting patients, a fresh tumor sample should be collected for biomarker analyses and processed. Whenever feasible, up to 3 cores will be obtained using 18 or 20 gauge needles as deemed appropriate by an Interventional Radiologist. The three cores will be processed as follows: 1) the first core biopsy specimen will be preserved in RNAlater for microarray studies; 2) second core will be formalin-fixed and paraffin-embedded for IHC; and 3) third core will be snap frozen for DNA, RNA, or protein isolation. FNA sample will be analyzed by flow cytometry. These samples will be transported in RNAlater (core # 1)/formalin (core # 2)/normal saline (cores # 3 and FNA) within 6 hours of collection on ice to [name] laboratory for processing at the [name], at MDACC. If fresh biopsies are not feasible, archival tissue from prior tumor biopsy may be used for biomarker studies.

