9.3.5 Exploratory Analyses

The objective is to identify predictive and pharmacodynamic biomarkers after therapy with rituximab plus lenalidomide with ibrutinib in subjects with previously untreated FL and marginal zone lymphoma.

- Immunophenotyping of PBMCs to determine alteration in immune cell subsets
 - PBMC will be stained with multiple antibodies and analyzed with up to 12-parameter flow cytometry.
- Identification of signaling pathways or biomarkers that predict sensitivity or resistance by gene expression profiling (GEP)
 - GEP will be performed on tumor biopsies obtained at baseline in consenting subjects to determine predictive biomarkers. The primary focus of the analysis of GEP data will be to evaluate the 41-gene effector T cell signature previously described [36]. But other gene signatures specific to other immune cell subsets and tumor signaling pathways,

developed by our group will also be explored. Univariate Cox analysis will test whether pretreatment levels of the signature significantly correlate with PFS. If so, techniques like leave-one-out cross-validation will be applied to assess the robustness of the signature, to the extent possible in a single dataset. We will also assess its significance as compared to the predictive power of random signatures. The baseline signature will also be tested in exploratory multivariate analysis with additional variables, principally the FLIPI score, and for its ability to predict complete response. Changes in signature levels post-treatment levels will be correlated with ultimate response, and, via landmark analysis, with PFS.

- Pharmacodynamic effects of combination therapy will be assessed in peripheral blood. Blood samples will be collected at baseline, Cycle 1, Day 1, Cycle 2, Day 1, and Cycle 7, Day 1. Lenalidomide affects multiple immune cell subsets and its effects may be assessed by multiparametric flow cytometry in PBMCs as previously described [24]. Since ibrutinib has been shown to inhibit ITK in Th2 cells and skew the polarization of CD4+ T cells to Th1 phenotype, we will also assess the ratio of Th1: Th2 cells in the PBMC by intracellular cytokine assay. Furthermore, alteration of various cytokines and chemokines will be assessed in the plasma by multiplex assays. The various cellular subsets measured at baseline will be compared with on-therapy time points and correlated with best clinical response and PFS

- Determination of alteration of cytokines and chemokines

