- l. All subjects will have bone marrow biopsy/aspirate performed at baseline (within 90 days of study entry). Subsequent bone marrow assessments will only be performed in subjects who have bone marrow involvement at baseline to confirm disease response (CR).
- m. Biomarker blood samples will be collected and processed as outlined in Section 7.4.18. On Cycle 1, Day 1, Cycle 1, Day 15, Cycle 2, Day 1 and Cycle 7, Day 1. Research blood test will be collected prior to rituximab dosing. At the time of documented PD, blood biomarker collection should be performed (\pm 4 weeks).
- n. If a fresh biopsy is being pursued as part of standard clinical practice, for consenting patients, fresh tumor can be collected as outlined in Section 7.4.19. If this is not possible, archival tumor tissue (paraffin embedded) when available should be collected at Screening for biomarker analyses for consenting patients. At the time of confirmed PD, if a tumor biopsy is planned as part of routine clinical practice, for consenting patients, a fresh tumor sample should be collected for biomarker analyses and processed as outlined in Section 7.4.19.
- o. Disease response assessment is based upon Cheson 2014 lymphoma response criteria. “Diagnostic quality” PET-CT with oral contrast/or water and IV contrast should be performed at Screening unless there is a contraindication or not covered by insurance. If CT scans have already been completed, a PET can be performed at Screening. PET/CT or CT and PET should be repeated to confirm complete remission and/or at treatment discontinuation if covered by insurance. For lymphomas that are not FDG-avid, PET does not need to be repeated in subsequent assessments. CTs of the neck, chest, abdomen, and pelvis with IV contrast will otherwise be conducted at baseline for those who do not undergo diagnostic quality PET-CT, at approximately Cycle 4, Day 1 (\pm 7 days), Cycle 7, Day 1 (\pm 7 days), at the completion of treatment and during the follow up phase. During the follow-up phase, response assessment should occur every 12 weeks (\pm 2 weeks) for 4 assessments, then every 24 weeks (\pm 4 weeks) until study completion, PD, withdrawal of consent, death, or lost to follow up, whichever comes first. When a contraindication prevents CT, an MRI of the chest, abdomen/pelvis can be substituted.

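### No tumor sample is scheduled between screening and progression, so the planned analysis of post-treatment change in the gene signature lacks the data it needs

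*Combined protocol and SAP*

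**What the plan says.** Section 9.3.5 places gene-expression profiling on tumor tissue: "GEP will be performed on tumor biopsies obtained at baseline in consenting subjects to determine predictive biomarkers". Its main focus is a 41-gene effector T-cell signature. The baseline level is to be tested against PFS by univariate Cox regression, examined alongside FLIPI, and assessed as a predictor of complete response. The same bullet then states: "Changes in signature levels post-treatment levels will be correlated with ultimate response, and, via landmark analysis, with PFS". It names no post-treatment tumor sample, no sampling time and no landmark time.

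Tumor tissue is described in these places:

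- **Screening.** Section 7.4.19 says that, in consenting patients, "core needle biopsies and fine needle aspirates (FNA) will be obtained at Screening by Interventional Radiology". Footnote n of the flow chart (13.1) adds a fallback: "archival tumor tissue (paraffin embedded) when available should be collected at Screening for biomarker analyses for consenting patients".
- **Progression.** Section 7.4.19 says: "For subjects with PD on radiologic assessment, a tumor biopsy to confirm PD is optional". Fresh research tissue is then collected from consenting patients under a condition: "At the time of confirmed PD, if a tumor biopsy is planned as part of routine clinical practice". Footnote n repeats that condition.
- **Early Treatment Termination Visit (7.2.8).** The list includes "Optional tumor tissue biopsy to document PD (Research biomarker assessment").

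The procedure lists for treatment visits (7.2.1 to 7.2.7), the End of Treatment Visit (7.2.9) and follow-up (7.3) contain no tumor biopsy. The serial research samples in 7.4.18 and 7.2.10 are blood.

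**The concern.** A landmark analysis relates a marker known by the landmark time to later events in patients who are still event-free then. Here the only later tumor sample that the plan specifies is triggered by the PFS event itself. The marker would become known when the patient leaves the risk set, so the named method has little or nothing to work on.

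The response part has a different weakness. Only progressors with a biopsy can supply a change value, and they supply it after their response is known. Patients in lasting remission, whose change would be of most interest, supply none. A result from that subset would describe biology at relapse, while the sentence would let it be reported as on-treatment change related to outcome.

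**Working it through.** **1. What the analysis needs.** Let S be the time of the post-baseline tumor sample, T the PFS time (9.3.2.1: first documented progression or death) and L the landmark. A patient contributes only if S ≤ L < T.

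**2. What the plan supplies.**

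| Time point | Tumor tissue | Source |
|---|---|---|
| Screening | Yes, with consent; fresh or archival | 7.1, 7.4.19, footnote n |
| Treatment visits | None listed | 7.2.1–7.2.7 |
| End of Treatment Visit | None listed in the text | 7.2.9 |
| Early termination | Optional, to document PD | 7.2.8 |
| Confirmed PD | With consent, if a routine biopsy is planned | 7.4.19, footnote n |
| Follow-up without PD | None listed in the text | 7.3 |

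On-treatment research blood is drawn at Cycle 1 Days 1 and 15, Cycle 2 Day 1 and Cycle 7 Day 1 (7.4.18). The blood assays described in 9.3.5 are flow cytometry, intracellular cytokine and multiplex assays. Gene-expression profiling on blood is not described.

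**3. Landmark PFS.** For a sample taken at confirmed PD, S ≥ T. The condition S ≤ L < T then cannot be met for any L. Only tissue obtained outside the PD rule could add a patient to the risk set.

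**4. Response.** A correlation can be computed among progressors with paired tissue, because their earlier best response may differ. The selection is on progression, and the change is observed after response has been determined.

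**5. Size.** Inputs from 9.5: n = 60, expected 2-year PFS 77%, accrual 4 per month.

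- Check of the plan's own figure: 1.96 × √(0.77 × 0.23 / 60) = 0.1065, which agrees with the stated half-width of 0.106. The point does not depend on it.
- PFS events by 2 years: 60 × (1 − 0.77) = 13.8.
- Events by the final analysis, assuming exponential PFS: hazard = −ln(0.77) / 2 = 0.1307 per year. Treatment is 12 × 28 days = 0.920 years, and the final analysis comes 3 years after the last patient's last dose (9.3.2.1). Patient i (0 to 59) enters at i/48 years and is followed for (59 − i)/48 + 0.920 + 3 years, from 5.149 years for the first patient to 3.920 for the last. Event probability runs from 1 − exp(−0.1307 × 5.149) = 0.490 to 1 − exp(−0.1307 × 3.920) = 0.401. The sum over 60 patients is 26.8 events, leaving 33.2 event-free.
- Paired samples if 25% to 75% of patients with an event have a biopsy (assumption): 13.8 × 0.25 = 3.5 to 13.8 × 0.75 = 10.4 by 2 years, and 26.8 × 0.25 = 6.7 to 26.8 × 0.75 = 20.1 by the final analysis. These are on the high side, because the event counts include deaths, which yield no PD tissue.

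Section 9.5 words the final analysis as 3 years of follow-up without tying it to the last dose. A shorter follow-up would give fewer than 27 events.

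**The case against.** A reader might infer that every patient with a post-treatment value must already have progressed, and that exactly no one is at risk. The documents do not go that far:

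- Footnote n opens by allowing fresh tissue to be collected whenever a biopsy is being done in standard practice, and gives no time limit. The archival fallback that follows names Screening, so the opening may be meant for screening only, but it does not say so.
- The tissue row of the flow chart carries three later marks. Column alignment is uncertain in the text form of the chart. If the row is shifted as the TSH row must be to agree with 7.2.8 and 7.2.9, the marks fall at Early Termination, End of Treatment and Follow-up. End of Treatment is for patients who complete therapy and is not a PD visit. The marks refer to footnote n, so they do not by themselves schedule a sample.
- A biopsy on suspected PD (7.2.8) may fail to confirm lymphoma. That patient stays at risk, though such tissue is of doubtful use for a tumor signature.

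It would also go too far to call the response correlation impossible or to predict a spurious association. The correlation is computable in a restricted group, and no direction of bias has been shown; imprecision from few pairs is at least as plausible.

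Two more points are fair. The analysis is exploratory, and 9.3.5 already plans to relate on-therapy blood subsets to best response and PFS. Both limit the consequence. Neither supplies the missing tumor sample.

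**Conclusion.** The point holds in a limited form. The plan commits to relating tumor-signature change to response and, by landmark, to PFS, yet it schedules no post-baseline tumor sample outside progression. The landmark risk set would be empty or nearly so, depending on incidental standard-practice biopsies. The response correlation would rest on biopsied progressors only, without durable responders.

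The pool of patients who could have paired tissue is below about 14 of 60 by 2 years and below about 27 by the final analysis. The first figure rests on the plan's expected 77%. The second also assumes exponential PFS, the planned accrual rate and follow-up to 3 years after the last dose. The sampling conclusion itself rests on none of these figures.

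This is a minor matter: one sentence in an exploratory section, with no effect on the primary or secondary endpoints, sample size or safety monitoring.

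**What to change.** In 9.3.5, remove the sentence relating signature change to response and landmark PFS. Replace it with a descriptive paired comparison of baseline and PD tissue, labelled as applying to progressors only, with the number of pairs reported. Keep the baseline-signature analyses as they are.

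Leave on-treatment change to the blood measures already planned. Where these are related to PFS, state a landmark at the sampling time, for example Cycle 7 Day 1, restrict the analysis to patients event-free at that visit, and count PFS from it.

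The cost is one revised sentence plus one on the blood landmark, with no new samples or visits. What is lost is an exploratory analysis that the planned samples cannot support. If the authors want to keep it, they would have to name the post-treatment material and its time point, which for tumor tissue would mean adding a sample.

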9.3.6 Handling of Biomarker Samples

Samples obtained for biomarker research including peripheral blood or tumor tissue will be maintained in [name] lab until study termination, at which time they will be destroyed as per institution policies.

9.4 Handling of Missing Data

Subjects lost to follow up will be included in the statistical analyses up to the point of their last evaluation or contact.

Data for subjects without disease progression or death will be censored at the date of the last tumor assessment and before the date of initiation of alternative anticancer therapy. Subjects with no post-baseline assessment will be censored on cycle 1, day 1.

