7.3.1 Survival Follow Up

Once subject progresses or starts use of alternative antineoplastic therapy (for subjects who have not withdrawn consent), they will be contacted approximately q 12 weeks (\pm 2 weeks) for 1 year and then q 24 weeks (\pm 4 weeks) from the last dose of study drug by clinic visit or telephone to assess survival and the use of alternative antineoplastic therapy and stem cell transplant. Subjects will be contacted until: death, consent withdrawal, lost to follow up, or study termination, whichever comes first.

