9.3.2.1 Analysis Methods

The primary analysis for all efficacy endpoints will be conducted based on the all treated population. PFS is defined as the time from the treatment start date (Cycle 1, Day 1) until the first date of objectively documented progressive disease or date of death from any cause. Patients will be censored at the last follow-up date if progression or death has not occurred during follow-up. If a patient has missing data (incomplete CT scan), all other available CT, PET/CT or MRI of the patient will be used for the analysis. Kaplan-Meier method will be used to estimate the PFS. Corresponding 95% CI will be summarized. Cox proportional hazards models will be used to assess the effects of patient prognostic factors on time-to-event endpoints. The final analysis will be performed when the last patient is followed for 3 years after last study drug dose.

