13. APPENDICES

13.1 Study Flow Chart

	Screening Phase	Treatment phase						End of Treatment		Follow up Phase
Treatment Cycle/Title	Screening Visit	1 ^a	2 ^a	3	To be repeated up to 12 cycles			Early Treatment Termination Visit	End of Treatment Visit	Follow up visits ^b
					4	5	6			
Scheduling Window ^c (Days)	-28 to -1	± 2	± 2	± 2	± 2	± 2	± 2	± 14	± 14	q 12 weeks (± 2 weeks) for the 1 year and then q 24 weeks (± 4 weeks)
Clinical/Administrative Assessments										
Informed Consent ^d	X									
Inclusion/Exclusion Criteria	X	X								
Demographics and Medical History	X									
Record FLIPI score	X									
Record Tumor burden	X									
Concomitant Medication Review ^e	X	Day 1, 8, 15, 22	Day 1, 15	X	X	X	X	X	X	
Drug accountability			X	X	X	X	X	X	X	
Rituximab Administration ^f		Day 1, 8, 15, 22	X	X	X	X	X			
Dispense ibrutinib and lenalidomide		X	X	X	X	X	X			
Review Adverse Events ^g		Day 1, 8, 15, 22	Day 1, 15	X	X	X	X	X	X ^g	X ^g
Physical Examination	X	Day 1, 8, 15, 22	Day 1, 15	X	X	X	X	X	X	X
Vital Signs and Weight ^h	X	Day 1, 8, 15, 22	Day 1, 15	X	X	X	X	X	X	X
ECOG Performance Status	X	Day 1, 8, 15, 22	Day 1, 15	X	X	X	X	X	X	X
ECG	X									
Laboratory Assessment										
Pregnancy Test – Serum b-HCG ⁱ	X									
PT/INR and aPTT ^j	X									
HIV 1 and 2 antibody	X									
HBsAg, anti-Hep Bc, Hep C Ab ^k	X									
CBC with Differential	X	Day 1, 8, 15, 22	Day 1, 15	X	X	X	X	X	X	X
Comprehensive Serum Chemistry Panel	X	Day 1, 8, 15, 22	Day 1, 15	X	X	X	X	X	X	X
Creatinine clearance (modified Cockcroft-Gault)	X	Day 1, 8, 15, 22	Day 1, 15	X	X	X	X			
TSH	X						X	X		
Bone marrow biopsy and aspirate ^l	X									
Biomarkers Blood Collection ^m		X	X				X ^m	X ^m	X ^m	
Biomarkers Tissue Collection ⁿ	X ⁿ						X ⁿ	X ⁿ	X ⁿ	
Radiologic Assessment										
Response Assessment: CT/PET/ or MRI ^o	X			X			X ^p	X	X	

Proprietary Information of MD Anderson

- a. For each Cycle, assessment is assumed to be on Day 1 unless otherwise specified.
- b. In subjects who discontinue study therapy without documented disease progression, every effort should be made to continue monitoring their disease status as per the follow-up schedule until (1) the start of new anti-cancer treatment, (2) documented disease progression, (3) death, or (4) the end of the study, whichever occurs first. Survival assessments will continue up to 3 years after the last study drug.

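### If Section 9.4 governs PFS censoring, a subject who starts new anticancer therapy is cut back only when no event follows, so censoring depends on the later outcome

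*Combined protocol and SAP*

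**What the plan says.** Section 9.3.2.1 (Analysis Methods) runs PFS from Cycle 1 Day 1 "until the first date of objectively documented progressive disease or date of death from any cause". It does not exclude events that follow a change of therapy. Its censoring rule is "Patients will be censored at the last follow-up date if progression or death has not occurred during follow-up", and the estimator is stated as "Kaplan-Meier method will be used to estimate the PFS".

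Section 9.4 (Handling of Missing Data) gives a second rule: "subjects without disease progression or death will be censored at the date of the last tumor assessment and before the date of initiation". What is initiated, in that sentence, is a different anticancer treatment. The cut-back to a scan before new therapy is therefore stated only for subjects with neither progression nor death.

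The sections on data collection after new therapy do not agree:

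- Flow chart footnote b (13.1), for subjects who stop treatment without progression, says "every effort should be made to continue monitoring their disease status as per the follow-up schedule until (1) the start of new anti-cancer treatment".
- Section 7.3.1 then arranges contact "to assess survival and the use of alternative antineoplastic therapy and stem cell transplant". Progression is not on that list.
- Footnote o of the same chart gives the reasons for ending response imaging, and new therapy is not among them.
- Section 8.2 has every subject who discontinues treatment followed for both progression and survival.

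**The concern.** Take two subjects who start the same new therapy at month 12, neither having progressed. One dies at month 40. The other is alive and progression-free at the cut-off. Under the literal text the first is an event at month 40, so counts as at risk and event-free throughout the first two years. The second is removed at the last scan before month 12. The only difference between them arose well after the 2-year mark, yet it decides how each contributes to the 2-year estimate.

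Kaplan-Meier needs the decision to censor to rest on what is known at the time of censoring. Here it rests on the future. Events after new therapy stay in the analysis while matching event-free time is dropped, and a larger sample would not remove the resulting bias. The estimate corresponds neither to following everyone regardless of new therapy nor to censoring everyone at new therapy. This is the primary endpoint of a single-arm study, so no control arm shares the distortion.

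**Working it through.** Three rules are compared. *Full follow-up* ignores new therapy for everyone. *Symmetric censoring* censors every starter at the last scan before new therapy. *Literal 9.4* does that only for starters with no later event.

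**1. The plan's own figure.** Section 9.5 gives N = 60, an expected 2-year rate of 77% and a 95% half-width of 0.106. The normal approximation gives 1.96 × √(0.77 × 0.23 / 60) = 0.1065, which agrees. This figure does not depend on the censoring rule and serves only as a yardstick.

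**2. A hand example (illustrative counts).** There are 60 subjects with 14 events by month 24. Six start new therapy at month 12, with their last scan at month 11. Two of the six have an event at month 18 and four stay event-free. Of the other 12 events, five fall before month 11 and seven after, so 55 are at risk at month 11.

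- Full follow-up: 46/60 = 0.767.
- Symmetric censoring: 55 − 6 = 49 remain, with 7 later events. 55/60 × 42/49 = 0.786.
- Literal 9.4: 55 − 4 = 51 remain, with 7 + 2 = 9 later events. 55/60 × 42/51 = 0.755.

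Literal 9.4 lies below both of the other estimates, not between them.

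**3. Simulation with an unchanged event rate.** From the documents: a constant hazard of −ln(0.77)/2 = 0.1307 per year. Accrual takes 60/4 = 15 months, and 12 cycles (about 11 months) plus 3 years gives about 47 to 62 months of follow-up; the run used 4.0 to 5.2 years. Scans were placed at weeks 12, 24, 52, 64, 76, 88 and 100. Assumed, because the documents do not give them: the share starting new therapy without progression, and start times between months 2 and 20. Each scenario had 1,000,000 subjects. 2-year PFS in %:

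| Share starting | Symmetric | Literal 9.4, all later events captured | Difference (points) | Difference if only deaths are captured (5% per year, assumed) |
|---|---|---|---|---|
| 5% | 76.9 | 76.6 | −0.3 | about −0.1 |
| 10% | 76.8 | 76.1 | −0.7 | about −0.2 |
| 20% | 76.6 | 75.2 | −1.4 | about −0.6 |

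**4. Simulation with a changed event rate.** A separate run had 400,000 subjects per scenario, new therapy starting at a constant rate, scans about every 12 weeks, and an event rate after new therapy of 1, 2 or 3 times the earlier one. Differences of literal 9.4 when all later events are captured, in points:

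| Share starting by 2 years | Below symmetric | Below full follow-up |
|---|---|---|
| 5% | 0.3 to 1.0 | 0.1 to 0.4 |
| 10% | 0.7 to 1.9 | 0.3 to 0.8 |
| 20% | 1.4 to 3.9 | 0.7 to 1.7 |

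If only deaths are captured after new therapy (death rate 0.05 to 0.2 of the PFS event rate, assumed), literal 9.4 is 0.03 to 0.3 points below symmetric censoring. Against full follow-up it is 0.1 to 0.6 points low when the event rate is unchanged, but 0.3 to 3.1 points *high* when the rate is 2 to 3 times higher, because later progressions go unrecorded. With the step 3 inputs, 10% starting and 3 times the rate, it gives 76.6% against 75.1% under full follow-up.

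**The case against.** The strongest reply is that this is a drafting consequence of a more basic conflict. Section 9.3.2.1, the primary-endpoint section, has its own rule with no cut-back, and under it the asymmetry disappears. That stands. It does not dispose of the point, because settling the conflict by adopting 9.4 as worded would keep the defect.

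Second, 9.4 may be loose wording for the usual rule that subjects event-free when new therapy starts are censored at the last prior scan. That is possible, but the text does not say so, and an analyst coding it as written would produce the asymmetric version.

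Third, the size is small. One subject in 60 is 1/60 = 1.7 points, the share starting new therapy is not in the documents, and the plan sets no null rate or decision threshold for 2-year PFS. This stands, and it limits the weight of the point.

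Fourth, event-free survival already counts new anti-lymphoma treatment as an event for everyone. That is a useful companion result, but it is a secondary endpoint and does not repair the primary one.

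Fifth, symmetric censoring is not neutral. With 2 to 3 times the event rate after new therapy, it gave 0.767 to 0.769 in step 4, against 0.735 to 0.765 under full follow-up. This also stands and is the reason for the sensitivity analysis.

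**Conclusion.** The point holds on a literal reading of 9.4 and only if 9.4 governs. Censoring then depends on the later outcome and the Kaplan-Meier estimate is biased. Against symmetric censoring the shift is downward in every scenario run, by the amounts in steps 3 and 4. All of these are well inside the 10.6-point half-width, so this is a correction that should be made and not a threat to the trial's conclusions. The sizes rest on assumed shares starting new therapy, a constant hazard before it, and assumed event and death rates after it.

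A reader might infer three stronger things that the documents do not support:

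- *PFS is always too low.* This holds only against symmetric censoring. Against full follow-up the estimate can be too high if later progressions are missed and the event rate rises.
- *Every event after new therapy is kept.* Only deaths are assured. Footnote b and 7.3.1 point to no disease monitoring after new therapy, while footnote o and 8.2 point the other way.
- *The defect exists whichever rule applies.* The last-follow-up rule in 9.3.2.1 does not have it.

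**What to change.** State one PFS censoring rule, in the same words in 9.3.2.1 and 9.4, and apply it to every subject whatever happens later. For example: *Any subject who starts alternative anticancer therapy before documented PD is censored at the last tumor assessment before that therapy, whether or not PD or death is recorded later.*

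Add a sensitivity analysis that ignores new therapy for everyone, using the progression and death data available and keeping later event-free follow-up as well as later events. Reconcile footnote b and 7.3.1 with footnote o and 8.2 on whether disease status is followed after new therapy.

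The cost is a short text change and one more Kaplan-Meier run, and the primary rule needs no new data. There are two limits. Censoring at new therapy may itself be informative, and somewhat optimistic if starters are at higher risk. The sensitivity analysis is only as good as the progression data collected after new therapy, so it is weak if that follow-up stops.
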